
	
against various resistotypes, irrespective of β-lactam and macrolide susceptibility, but also minimize the risk of resistance emergence or induction of cross-resistance to other agents. A new ketolide antibiotic with improved coverage of MDR pathogens—especially respiratory pathogens that are resistant to the older macrolides —would help address this unmet need.
 
In all, nafithromycin is expected to have the following advantages over older, available macrolides based on data from in vivo, in vitro and preclinical studies conducted to date:
 
 1. Mechanism-based activity potential against macrolide- and ketolide-resistant pneumococci and Group A streptococci 2. Excellent target-organ-tissue concentration leading to: 
 a. Enabling potent activity vs. MDR pathogens in vivo b. Once-a-day dosing convenience c. Potential for shorter duration of therapy 3. Minimal CYP inhibition leading to ease of co-administration of other drugs 4. Favorable hepatic safety potential owing to favorable drug disposition resulting from lower accumulation in liver 5. Comprehensive coverage of all key CABP pathogens, including atypical pathogens

Objectives
	
Primary Objectives:
 
 • To assess the overall safety and tolerability of oral nafithromycin • To assess the clinical response in the Intent-to-Treat (ITT) population at Day 4 
Secondary Objectives:
 
 • To assess the clinical response in the Microbiological Intent-to-Treat (micro-ITT) population at Day 4 • To assess the clinical outcome in the ITT and Clinically Evaluable (CE) populations at End-of-Treatment (EOT) and Test-of-Cure (TOC) (Day 15 \pm 3 days) • To assess early improvement in clinical symptoms and normalization of vital signs in the ITT population at Day 4 • To assess clinical outcome in micro-ITT population at TOC • To assess by-subject and by-pathogen microbiological response in micro-ITT and microbiologically evaluable (ME) populations at TOC • To assess readmission to the hospital (or admission to the hospital if not previously hospitalized) for any reason prior to Follow-Up (FU)

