Statistical Methods	
Efficacy
 
Efficacy will be analyzed in the following populations according to the random treatment assignment:
 
 • ITT population: All subjects who were randomized • micro-ITT population: All ITT subjects who have at least one baseline Gram-positive or atypical bacterial pathogen known to cause CABP, including bacterial pathogens identified by respiratory specimen culture, blood culture, urinary antigen test (S. pneumoniae, L. pneumophila), or atypical bacterial serologic response (M. pneumoniae, C. pneumoniae, L. pneumophila). Subjects with sole baseline Gram-negative bacterial infection will be excluded from this population. • Clinically evaluable (CE) population: ITT population that follows important components of the trial (criteria provided in Section 16.1.4) • ME population: Micro-ITT population that follows important components of the trial (criteria provided in Section 16.1.5) 
This study is not powered for inferential statistical analyses. All data will be summarized separately by study drug (nafithromycin for 3 days, nafithromycin for 5 days, and moxifloxacin). Descriptive statistics (mean, standard deviation, median, minimum, and maximum) will be presented for continuous variables. Frequency distributions (counts and percentages) will be presented for categorical variables. All summaries will be presented within each treatment group. The 95% confidence intervals, obtained using the Clopper-Pearson method, for the proportions of subjects with a favorable response in each treatment group will be presented.
 
Safety: Safety data will be summarized for the Safety population, which includes all randomized subjects who received any amount of study drug, analyzed according to the treatment received. The subject incidence of serious adverse events (SAEs), including deaths and discontinuations due to adverse events (AEs) will be presented by system organ class and preferred term according to the Medical Dictionary of Regulatory Activities (MedDRA[®]), relationship to study drug, and severity.
 
PK: The PK data acquisition and analysis strategy entails the use of a sparse PK sampling schedule. Efforts will be made to obtain PK samples from all subjects at sites where PK sampling is possible. Plasma concentrations of nafithromycin will be listed for each subject in the PK Population. Nafithromycin plasma concentration data, along with other information including demographic data, will be combined with appropriate data from other clinical studies and analyzed using a population PK approach and reported separately.

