8.0 STUDY DESIGN

8.1 TYPE OF STUDY

This is a Phase II prospective, multicenter, multinational, randomized (1:1:1), double-blind, comparative study to determine the efficacy, safety, tolerability, and PK of oral nafithromycin versus oral moxifloxacin for treatment of adults with CABP. Study drug is defined as oral nafithromycin tablets or oral moxifloxacin capsules. Relevant matching placebo formulations (tablets and capsules) are used to maintain the blind.

Subjects providing informed consent and meeting all study eligibility criteria will be randomized into the study in a 1:1:1 ratio to either of the following 3 treatment arms:

- Arm A: Nafithromycin 800 mg (two 400 mg tablets) PO q24h for 3 days; subjects will receive matching placebo (two nafithromycin placebo tablets PO q24h) on Days 4 through Day 7, and one moxifloxacin placebo capsule PO q24h on Days 1 through 7, to maintain the blind
- Arm B: Nafithromycin 800 mg (two 400 mg tablets) PO q24h for 5 days; subjects will receive matching placebo (two nafithromycin placebo tablets PO q24h) on Day 6 and Day 7, and one moxifloxacin placebo capsule PO q24h on Days 1 through 7, to maintain the blind
- Arm C: Moxifloxacin 400 mg (one 400 mg over-encapsulated tablet) PO q24h for 7 days; subjects will also receive two nafithromycin placebo tablets PO q24h on Days 1 through Day 7, to maintain the blind

Baseline assessments for study eligibility will occur within 24 h prior to randomization using IXRS, stratified by region (US vs. ex-US) and PORT Risk Class (II vs. III/IV), will be used to assign subjects (1:1:1) to Arm A, Arm B or Arm C. Study Day 1 is defined as the day that the study drug is first administered, and subsequent study days are defined by the number of consecutive calendar days thereafter.

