- Progression of disease or insufficient therapeutic effect which causes new hospitalization (in subjects not previously hospitalized for the index CABP), rehospitalization (in subjects that were previously hospitalized for the index CABP and discharged); however, if this leads to death, it should be recorded as a serious adverse event (SAE) ([Section 14.1.3](#)).

A TEAE is defined as an AE or SAE that occurs during or after the first administration of study drug and up through the FU visit.

A life-threatening AE is an AE that, in the view of either the Investigator or Sponsor, places the subject at immediate risk of death. It does not include an AE that, had it occurred in a more severe form, might have caused death.

An AE is considered “unexpected” if it is not listed in the IB or is not listed at the specificity or severity that has been observed; or, if an IB is not available, is not consistent with the risk information described in the general investigational plan. For example, under this definition, hepatic necrosis would be unexpected (by virtue of greater severity) if the IB referred only to elevated hepatic enzymes or hepatitis. Similarly, cerebral thromboembolism and cerebral vasculitis would be unexpected (by virtue of greater specificity) if the IB listed only cerebral vascular accidents. “Unexpected,” as used in this definition, also refers to AEs that are mentioned in the IB as occurring with a class of drugs or as anticipated from the pharmacological properties of the drug, but are not specifically mentioned as occurring with the particular drug under investigation. Progressive worsening of the index CABP or insufficient therapeutic effect of study drug that leads to hospitalization or death (i.e., SAE criteria, [Section 14.1.4](#)) is considered expected—as part of potential disease progression—and not unexpected.

Some AEs are listed in the IB as occurring with the same class of drugs, or as anticipated from the pharmacological properties of the drug, even though they have not been observed with the drug under investigation. Such events would be considered unexpected until they have been observed with the drug under investigation.

The list of AEs included in the current version of the Investigator’s Brochure will be used as reference safety information.

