16.2.4 Safety Analyses

Evaluation of the safety and tolerability of oral nafithromycin for 3 or 5 days in the treatment of CABP is an important primary objective for this Phase II study. Safety will be analyzed in the Safety Population ([Section 16.1.1](#)). Subjects in the Safety Population will be analyzed according to the treatment actually received.

Safety will be evaluated by presenting summaries of AEs, physical examinations, vital signs, laboratory evaluations (hematology evaluation, chemistry panel, UA, and ECG parameters). For each safety parameter, the last assessment made prior to the first administration of study drug will be used as the baseline value for all analyses.

The incidence of TEAEs (defined in [Section 14.1.1](#)) will be presented by system organ class and preferred term according to MedDRA®, by relationship to the administration of study drug, and by severity. In addition, the incidence of SAEs and AEs leading to discontinuation of study drug will be presented by system organ class, preferred term, and relationship to study drug. If the incidence of SAEs and AEs leading to discontinuation of study drug is low, only a listing will be provided.

Descriptive statistics of vital signs at each time point measured, as well as the change from baseline and PCS changes, will be presented. Descriptive statistics for ECGs and physical examinations will also be presented for each time point measured. The number and percentage of subjects with a normal physical exam result at baseline and an abnormal physical examination result at a follow-up assessment will be provided for each time point. Descriptive statistics for clinical laboratory tests and vital signs and for the change from baseline will be presented by study visit. Potentially clinically significant clinical laboratory results will be determined based on normal limits and percent change from baseline.

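### Cheap improvement: TEAEs are tabulated over one window from first dose to follow-up, so the days on which 3 and 5 days of nafithromycin can differ are not shown separately

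*Combined protocol and SAP*

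**What the plan says.** - **Objective.** The first primary objective (synopsis and Section 7.1) is "To assess the overall safety and tolerability of oral nafithromycin". Section 16.2.4 restates it as safety for 3 or 5 days of treatment and calls it an important primary objective.
- **Reporting groups (synopsis, Statistical Methods; repeated in Section 16.2).** "All data will be summarized separately by study drug (nafithromycin for 3 days, nafithromycin for 5 days, and moxifloxacin".
- **Regimens (Section 8.1).** Arm A is "Nafithromycin 800 mg (two 400 mg tablets) PO q24h for 3 days"; Arm B is "Nafithromycin 800 mg (two 400 mg tablets) PO q24h for 5 days". Both are filled with placebo to Day 7, and both take moxifloxacin placebo throughout. Active treatment is the same on Days 1-3 and differs only on Days 4-5.
- **TEAE window (Section 14.1.1).** An event counts if it "occurs during or after the first administration of study drug and up through the FU visit". Section 8.4 puts follow-up at Day 28 to Day 34.
- **TEAE tables (Section 16.2.4).** Incidence by system organ class and preferred term, "by relationship to the administration of study drug, and by severity". SAEs and AEs leading to discontinuation are presented as well. No onset period is named.
- **Other safety data (Section 16.2.4).** Laboratory tests and vital signs are summarised by visit, and ECGs and physical examinations by time point.
- **Status of comparisons (Section 16.2).** The study is exploratory and no formal comparison between groups is planned. A separate SAP is to be finalised before database lock; its text is not in the file.

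**The concern.** A reader choosing a Phase 3 regimen will set the Arm A and Arm B columns side by side. Each TEAE percentage mixes three days of identical treatment, the two days that differ, and more than three weeks in which neither arm takes nafithromycin. Events from the shared periods add the same expected count to both arms, plus noise.

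The relationship split does not isolate the days of interest. Section 14.1.2 bases relatedness largely on timing relative to study treatment, but sites are blinded (Section 10.6) and every subject takes tablets and a capsule for seven days. The Investigator cannot know that Arm A's tablets from Day 4 are placebo.

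At stake is how much the trial can say about the tolerability of two further days of drug. TEAEs are the one main safety measure that the plan does not show over time.

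**Working it through.** **The plan's own figure.** None is given for TEAEs. The only precision figure (Section 16.2.1: 66.9% to 86.7% around a 78% Day 4 response, n = 75) is for efficacy. It reproduces as a Clopper-Pearson interval at 0.78 × 75 = 58.5 responders (66.9% to 86.7%) and has no bearing on this point.

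**Day count (Sections 8.1 and 8.4), follow-up at Day 31.**
- Days on which active drug differs: 2/31 = 6.5%.
- Days 1-3, identical: 3/31 = 9.7%.
- Day 6 to Day 31, after both arms' last active dose: 26/31 = 84%.

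**Inputs.** n = 75 per arm (Section 8.3). *Assumed, because the documents give no TEAE rates:* constant daily hazards, background *b* = 0.5%, 1% or 2%, and excess *e* = 2%, 3% or 5% per day while active drug has effect. Carry-over *c* is 0 or 2 days after the last active dose, the same in both arms. The synopsis gives a half-life of about 11 h, so about 0.5^(48/11) = 5% of plasma drug remains after 48 h. The full window is taken as 30 days.

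**Formulas.** Incidence = 1 − exp(−H), with:
- Full window: H_A = 30b + (3 + c)e; H_B = 30b + (5 + c)e.
- Onset Days 4-7: H_A = 4b + ce; H_B = 4b + (2 + c)e.
- SE = √{[p_A(1 − p_A) + p_B(1 − p_B)]/75}.

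**Main example, b = 1%, e = 3%** (differences taken before rounding):

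| Window | Carry-over | H_A, H_B | Arm A | Arm B | Difference (points) | SE (points) | Difference/SE |
|---|---|---|---|---|---|---|---|
| First dose to FU | none | 0.39, 0.45 | 32.3% | 36.2% | 3.9 | 7.7 | 0.51 |
| Onset Days 4-7 | none | 0.04, 0.10 | 3.9% | 9.5% | 5.6 | 4.1 | 1.38 |
| First dose to FU | 2 days | 0.45, 0.51 | 36.2% | 40.0% | 3.7 | 7.9 | 0.47 |
| Onset Days 4-7 | 2 days | 0.10, 0.16 | 9.5% | 14.8% | 5.3 | 5.3 | 0.99 |

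The gain is 1.38/0.51 = 2.7 without carry-over and 0.99/0.47 = 2.1 with two days of it. Most of it comes from the smaller SE.

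**Whole grid (nine combinations of b and e).** The gain is 2.5 to 3.1 times without carry-over and 1.8 to 2.7 times with two days, whether the full window is counted as 30 or 31 days. Difference/SE for Days 4-7 exceeds 1.96 in 2 of 9 combinations without carry-over and in none with two days.

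**Days 1-3.** Because Arms A and B are identical there, they can also be combined. At b + e = 4% per day, incidence is 1 − exp(−0.12) = 11.3%. The 95% half-width, 1.96√(0.113 × 0.887/n), is 7.2 points at n = 75 and 5.1 points at n = 150.

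**The case against.** The strongest reply is that the plan sets up no test of Arm A against Arm B. The objective is overall safety, Section 16.2 rules out formal comparisons, and table detail can still be settled in the SAP. That stands as far as it goes. The proposed table is descriptive and needs no test. But Section 16.2.4 does specify the TEAE tables, and an onset split is more credible if stated before unblinding than if chosen afterwards.

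Second, the hazards are assumed, and drug effect may outlast dosing: the synopsis reports accumulation in cells and lung levels above plasma throughout the 48 h after a third dose. This also stands, which is why the two-day carry-over case is shown. The gain shrinks but remains in every combination tried.

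Third, late events matter for safety. They do, and the full-window table should stay.

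A reader might infer more than the documents support:
- *That the whole safety comparison is hidden.* It is not. TEAEs are also split by relationship and severity. ECGs (Days 3, 5 and EOT), vital signs and examinations (daily to Day 5, then EOT) and laboratory tests (Day 5 and EOT) are shown over time and bracket the days that differ.
- *That a subject in Arm B who stops by Day 3 moves to the Arm A column,* because the Safety population is one "which includes all randomized subjects who received any amount of study drug, analyzed according to the treatment received" and the columns are named by days of drug. Those names are arm labels. Arm A's regimen is three active days followed by four of matching placebo, so such a subject received a shortened Arm B course. Nothing in the documents says that early stoppers change column.

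**Conclusion.** The point holds as a cheap improvement to the stated analysis. The one period in which a TEAE difference between 3 and 5 days can first arise is not shown separately, although onset relative to dosing is already needed to define a TEAE.

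The cost is precision. A randomised contrast over the full window is not biased by shared events, so it would be wrong to conclude that the planned table misleads in a particular direction. It would also be too strong to say that a real difference is bound to be lost, because that depends on TEAE rates the documents do not give. Under the assumed rates the Day 4-7 table makes the contrast about 2.5 to 3.1 times sharper, or 1.8 to 2.7 times with two days of carry-over. Even so, in most combinations the difference stays below 1.96 standard errors at 75 per arm. The added table would inform judgement on duration; it would not settle it.

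**What to change.** In Section 16.2.4, keep the first-dose-to-follow-up TEAE table and add one descriptive table by onset period:

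1. Days 1-3: each arm, and Arms A and B combined beside Arm C.
2. Day 4 to Day 7: by arm.
3. After Day 7 to follow-up: by arm.

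In each period, count subjects with at least one event starting in that period. The denominator is subjects in the Safety population still under observation at the start of the period, so that those who left earlier do not dilute the later rows. Carry the same wording into the SAP before unblinding.

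Cost: one extra table and a few lines of text. Table 3-1 already has AEs recorded on each of Days 1 to 7, at TOC and at follow-up, so no new data or subjects are needed. The downside is small counts per period, so the table should be read as description only.

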FVC	forced vital capacity
GCP	Good Clinical Practice
h	Hours
HABP	hospital-acquired bacterial pneumonia
HCAP	healthcare-associated pneumonia
HIV	human immunodeficiency virus
IB	Investigator's Brochure
ICF	informed consent form
ICH	International Conference on Harmonisation
IDSA	Infectious Diseases Society of America
IMP	Investigational Medicinal Product

IMPD	Investigational Medicinal Product Dossier
ITT	Intent-to-Treat
IV	intravenous(ly)
IXRS	interactive voice/web response system
LPF	low power field
MDR	multidrug-resistant
ME	Microbiologically Evaluable
MedDRA	Medical Dictionary for Regulatory Activities
MIC	minimum inhibitory concentration
micro-ITT	Microbiological Intent-to-Treat population
MLS _B	macrolide, lincosamide and streptogramin B
PaO ₂	partial pressure of arterial oxygen
PD	pharmacodynamic
PK	pharmacokinetic
PMN	polymorphonuclear cell
PO	per os (by mouth)
PORT	Pneumonia Outcomes Research Team
QT	time from electrocardiogram Q wave to the end of the T wave
QTcF	QT interval corrected for heart rate using Fridericia's formula
rRNA	ribosomal ribonucleic acid
SAE	serious adverse event
SI	Système International d'Unités
T _½	half-life
TEAE	treatment-emergent adverse event
T _{max}	time at which drug is present at maximum concentration in serum
TOC	Test-of-Cure
ULN	upper limit of normal
US	United States
VABP	ventilator-associated bacterial pneumonia
WBC	white blood cell

6.0 **BACKGROUND AND RATIONALE**

6.1 **COMMUNITY-ACQUIRED BACTERIAL PNEUMONIA AND UNMET MEDICAL NEED**

Lower respiratory tract infection, including community-acquired bacterial pneumonia (CABP), remains the second largest cause of death and years of life lost worldwide; its associated age-standardized death rate was 41.7 per 100,000 population in 2013 ([GBD, 2015](#)). The global incidence of pneumonia is estimated to be between 1.5 and 14.0 cases per 1000 person-years, varying by region, season, and patient characteristics ([File, 2010b; Millett, 2013](#)). Short-term mortality (in-hospital and 30-day mortality) for hospitalized patients with CABP ranges from 4.0% to 18.0% ([Arnold, 2013; File, 2010b](#)). Costs related to community-acquired pneumonia are high, and few approaches (such as reducing the length-of-stay, adequate use of antibiotics, and the introduction of vaccines) have reduced these costs to date ([Prina, 2015](#)). *Streptococcus pneumoniae* remains the most common pathogen of CABP worldwide, independent of age. Other frequent causes of CABP include *Haemophilus influenzae*, *Moraxella catarrhalis*, and atypical bacteria (including *Mycoplasma*, *Chlamydia*, and *Legionella* spp.).

A major therapeutic challenge impacting the treatment of CABP is the widespread resistance of *S. pneumoniae* to β -lactams (especially penicillins and 1st and 2nd-generation cephalosporins) and macrolide antibiotics. For example, the prevalence of *S. pneumoniae* macrolide resistance on a global scale is estimated to be 25% to 40%, varying by region ([Farrell, 2008; Reinert, 2009](#)). The prevalence of multidrug-resistant (MDR) *S. pneumoniae*, defined by penicillin nonsusceptibility plus resistance to two additional non- β -lactam antibiotic classes, is also worrisome. For example, in the US, an analysis of 1498 clinical pneumococci strains collected between 2012 and 2013 found that 21.0% were MDR ([Richter, 2014](#)). Community-acquired MDR *S. pneumoniae* poses treatment challenges for outpatient CABP—most notably the lack of effective oral antibacterial options—because of resistance to the most commonly-used oral penicillins, cephalosporins, and/or macrolides. Failure of therapy due to resistance will continue to contribute to the morbidity and mortality of CABP, and treatment failures of mild disease will result in increased hospitalizations and contribute to increased healthcare costs.

The development of oral nafithromycin (described below in [Section 6.2](#)), which has activity against MDR *S. pneumoniae*, *Streptococcus pyogenes*, respiratory Gram-negative pathogens, and atypical pathogens, would provide clinicians with a new treatment option for CABP caused by the most common etiologies of CABP, including MDR *S. pneumoniae*, while maintaining an acceptable safety profile.

6.2 NAFITHROMYCIN

Nafithromycin (previously known as WCK 4873) is an IV and oral antibacterial agent of the ketolide class that is structurally related to the macrolide class. Diverse in vitro, in vivo, preclinical pharmacokinetic (PK) and safety studies have provided strong scientific evidence of the therapeutic potential of nafithromycin for difficult to treat respiratory tract infections caused by MDR pathogens. [REDACTED]

[REDACTED]

[REDACTED]

[REDACTED]

[Redacted text block]

[Redacted text block]

[Redacted text block]

- [Redacted list item]
- [Redacted list item]
 - [Redacted sub-item]
 - [Redacted sub-item]
 - [Redacted sub-item]
- [Redacted list item]
- [Redacted list item]
- [Redacted list item]

Refer to the current nafithromycin Investigator's Brochure (IB) for additional information regarding relevant nonclinical, microbiology, pharmacology and clinical studies.

